9.2. Vital signs

Vital signs will be measured by a qualified staff member at Visit 1, Visit 9 and Visit 13. The following items will be measured:

- Body temperature
- Pulse rate
- Respiration rate
- Blood pressure (systolic and diastolic) after the subject sits quietly for at least 5 minutes
- Height (at Visit 1 only)
- Weight (at Visit 1 only).

Any measure that is, in the opinion of the investigator, abnormal AND clinically significant (CS must be recorded as history if found prior to the first study medication treatment or as an AE if found after the first study medication treatment begins (Section 10.1).

A systolic blood pressure >140mm Hg or a diastolic blood pressure >90mm Hg is considered abnormal and therefore must be defined as CS or not clinically significant (NCS) on the CRFs.

9.3. Clinical laboratory sampling

Non-fasting blood samples for clinical laboratory analysis will be collected by a qualified staff member at Visit 1, Visit 9 and Visit 13. Approximately 7.5 mL of blood will be collected for each chemistry sample and 3 ml of blood will be collected for the complete blood count (CBC). These blood samples will be sent to a central laboratory for analysis. Refer to the study specific laboratory manual for instructions regarding handling of the blood samples and shipping instructions.

The following tests, at a minimum, will be conducted:

Chemistry Panel	Complete Blood Count	
Albumin	Hematocrit	
Alkaline phosphatase	Hemoglobin	
Alanine aminotransferase (ALT)	Platelet count	
Aspartate aminotransferase (AST)	Red blood cell morphology	
Blood urea nitrogen (BUN)	Red blood cell count	
Bicarbonate	White blood cell count	
Calcium	White blood cell differential	
Chloride	% & absolute	

Page 37 of 53 Amendment 2 Version 3 Date: 05 December 2017

- Creatinine Glucose Lactate dehydrogenase (LDH) Phosphorus Potassium Sodium Total bilirubin Total protein Uric acid
- Basophils Eosinophils Lymphocytes Monocytes Neutrophils

The results of the clinical laboratory tests will be reported on the central laboratory's standard reports. These laboratory results will be sent to the investigator via fax. The investigator must review all laboratory reports in a timely manner and note NCS or CS to define the clinical relevance of any result that is outside the normal range for the laboratory. The investigator must date and initial every laboratory report.

The investigator must review the Visit 1 laboratory results for all the measured analytes for each subject prior to Visit 2. The subject must not be randomized at Visit 2 if any of the Visit 1 results are outside normal range for the laboratory AND, in the opinion of the investigator, CS.

The investigator must report all laboratory results that are BOTH outside the normal range for the laboratory AND, in the opinion of the investigator, CS as medical history if found prior to the first study medication treatment or as an AE if found after the first study medication treatment begins.

9.4. Urine pregnancy tests

The investigator or designee will perform a urine pregnancy test for subjects who are WOCBP at Visit 1, at Visit 2 prior to randomization, Visit 9 and Visit 13.

Subjects who are WOCBP must have a negative pregnancy test result at Visit 1 to continue in the study and at Visit 2 to be randomized.

If the result of any post-randomization urine pregnancy test is positive, the subject will be withdrawn from the study and the subject's pregnancy documented and followed as outlined in Section 11.

9.5. Other Evaluations

9.5.1. Demographics and medical history

At Visit 1, the investigator or designee will collect demographic information including date of birth, sex at birth, race and, if appropriate, ethnicity for each subject.

At Visit 1, the investigator must determine each subject's Fitzpatrick skin type and document appropriately on the subject's CRF.

Skin Type	Description		
Classification	-		
Type I	always burns, never tans (pale white; blond or red		
	hair; blue eyes; freckles)		
Type II	ype II usually burns, tans minimally (white; fair; blond		
	red hair; blue, green, or hazel eyes)		
Type III	sometimes mild burn, tans uniformly (cream white;		
	fair with any hair or eye color)		
Type IV	burns minimally, always tans well (moderate brown)		
Type V	very rarely burns, tans very easily (dark brown)		
Type VI	Never burns, never tans (deeply pigmented dark		
	brown to darkest brown)		

Table 3 Fitzpatrick Skin Type Scoring System

(Fitzpatrick 1988)

Medical history information will be recorded including all medical conditions and disease states that, at Visit 1:

- Are ongoing
- Require concomitant therapy
- Are, in the opinion of the investigator, relevant to the subject's study participation.

9.5.2. Standardized photography

At Visits 1, 2, 4, 9, 10 and 13, a qualified investigational center staff member, other than the investigator, will take standardized color photographs of each Target and Non-Target Wart.

The photographs are to document the location of the Target and Non-Target Warts and to assist with relocating the Target/Non-Target Warts. The Target/Non-Target Wart ID stickers must be visible in the photographs. The subject's identity will not be revealed in the study photographs.

At Visit 2, the photographs must be taken prior to the study medication treatment.

Care must be taken to ensure the same lighting, background, and subject positioning relative to the camera and camera settings are used for each photograph.

Equipment, supplies, training and detailed instructions for obtaining and managing the photographs will be provided to the investigational center prior to the initiation of subject enrollment.

10. ADVERSE EVENTS

10.1. Definitions

10.1.1. Adverse events (AE)

- An adverse event (AE) is any untoward medical occurrence in a patient that develops or worsens in severity during the conduct of a clinical study of a pharmaceutical product and does not necessarily have a causal relationship to the study drug. An adverse event can, therefore, be any unfavorable and unintended physical sign, symptom, or laboratory parameter that develops or worsens in severity during the course of the study, or significant worsening of the disease under study (or any concurrent disease), whether or not considered related to the study drug. Accordingly, an adverse event could include any of the following:
- intercurrent illnesses
- physical injuries
- events possibly related to concomitant medication
- significant worsening (change in nature, severity, or frequency) of the disease under study or other pre-existing conditions. (NOTE: A condition, recorded as pre-existing, that is intermittently symptomatic [e.g., headache] and which occurs during the study should be recorded as an adverse event.)
- drug interactions
- events occurring during diagnostic procedures or any washout phase of the study
- laboratory or diagnostic test abnormalities occurring after the start of the study (i.e., after screening and once confirmed by repeat testing) that results in the withdrawal of the patient from the study, requires medical treatment or further diagnostic work-up, or is considered by the study investigator to be clinically significant. NOTE: Abnormal laboratory test results at the screening visit that preclude a patient from entering the study or receiving study treatment are not considered adverse events, but will be recorded to monitor data from patients who do not meet screening criteria.

Worsening of any of the Target or Non-Target Wart assessments should be reported as an AE ONLY if the use of the study medication is interrupted or discontinued or if therapy is required to manage the event.

The investigator must, for any Target or Non-Target Wart related AE, question the subject in detail to determine if there are any confounding factors (*e.g.*, irritation by clothing or activity, sunburn) for any such AE.

Page 40 of 53 Amendment 2 Version 3 Date: 05 December 2017 The investigator should, when certain, report a diagnosis rather than the signs, symptoms or clinically relevant abnormal laboratory values associated with the AE. Otherwise, signs, symptoms or abnormal laboratory values may be used to describe the AE.

Any CS abnormality discovered prior to the first study medication treatment should be reported as medical history, not as an AE.

10.1.2. Serious adverse event (SAE)

A Serious Adverse Event is any untoward medical occurrence that at any dose:

- Results in death
- Is life threatening
- Requires inpatient hospitalization or prolongation of existing hospitalization
- Results in persistent or significant disability/incapacity,
- Is a congenital anomaly/birth defect or
- Is an important medical event.

The term "life threatening" refers to an event in which the subject was at risk of death at the time of event; it does not refer to an event that hypothetically might have caused death if it was more severe.

Inpatient hospitalization is considered to have occurred if the subject is admitted to the hospital on an in-patient basis, even if released the same day. Prolongation of hospitalization is defined as an additional night stay in the hospital. Hospitalization for elective treatment of a pre-existing condition that did not worsen from baseline is not considered an AE.

Important medical events are those that may not be immediately life threatening, result in death or hospitalization, but are clearly of major clinical significance and may jeopardize the subject or require intervention to prevent one of the outcomes listed in the SAE definition above. These should also usually be considered serious. Examples of such events are intensive treatment in an emergency room or at home for allergic bronchospasm, blood dyscrasia or convulsions that do not result in hospitalization.

10.1.3. Adverse event reporting period

The investigator must start reporting non-serious AEs starting with the subject's first study medication treatment continuing until Visit 11. Non-serious adverse events that occur between the time the subject was consented and the first application of study medication will be reported as medical history.

Reporting for SAEs begins after the subject signs the informed consent and continues until Visit 11 (regardless of relationship to study medication). If a subject experiences a SAE after Visit 11 that is deemed by the investigator to be related to study medication, the investigator must report this to the Sponsor using the study specific SAE report form.

Page 41 of 53 Amendment 2 Version 3 Date: 05 December 2017

10.1.4. Severity

The investigator must define the severity of each AE using the following definitions as a guideline. The investigator will consider the range of the possible severity of the event and identify the severity that is the most appropriate according to her/his medical judgment.

Mild – Awareness of signs or symptom, but easily tolerated

Moderate – Discomfort, enough to cause interference with usual activity

Severe – Incapacitating with inability to perform usual activity.

10.1.5. Relationship to study medication

The investigator will determine if there is a reasonable causal relationship between the study medication and an AE or not. The investigator will use her/his best medical judgment and consider all relevant factors (*e.g.*, temporal relationship, location of the event, the subject's relevant medical history, concomitant therapies and concurrent conditions) to determine the relationship of the AE to the study medication. The investigator will define the relationship of an AE to the study medication by selecting one of the following categories:

Related – There is a reasonable possibility that there is a causal relationship between the study medication and the AE.

Not Related – There is not a reasonable possibility that there is a causal relationship between the study medication and the AE.

The term "reasonable causal relationship" means there are facts or arguments to suggest a causal relationship (International Conference on Harmonization (ICH) E2A).

10.2. Reporting Procedures

10.2.1. Procedures for reporting adverse events

At each post enrollment visit, the investigator or designee will question the subject to elicit AEs using a non-directive question such as "Has there been any change in your health since the previous study visit?"

The Investigator/designee will monitor the subject for at least 20 minutes after the Treatment Completion Time at any visit during which a study medication treatment is performed to elicit AEs in a similar manner.

If appropriate, based on the subject's response to non-directed questioning regarding AEs, the investigator or designee will follow-up with directed questions and appropriate evaluations.

Any AE noted during the reporting period must be reported in the source documents and on the appropriate AE CRF.

Page 42 of 53 Amendment 2 Version 3 Date: 05 December 2017 AEs that are defined as "Not Related" to the study medications will be followed until they are resolved or until the subject's last study visit. AEs that are defined as "Related" to the study medications will be followed until they are resolved or, if not resolved after the subject's last study visit, until in the opinion of the investigator, the AE reaches a clinically stable outcome with or without sequelae.

10.2.2. Procedure for reporting a serious adverse event

Upon becoming aware of a SAE occurring during the AE reporting period, whether or not related to the study medications, the investigator must:

- 1. Take the appropriate medical action to ensure the subject's safety
- 2. Immediately inform the Medical Monitor of the SAE:

[name] Symbio Main Number: [contact] Office Number: [contact] [contact] Serious Adverse Event [contact] Email: [contact]

- 3. Within 24-hours of becoming aware of the event, a SAE report form, an AE CRF and any other relevant information (*e.g.*, concomitant medication CRF, medical history CRF, laboratory test results) must be faxed to the SAE Fax line listed above.
- 4. Monitor and document the progress of the SAE until it resolves or, if not resolved after the subject's last study visit, until in the opinion of the investigator the AE reaches a clinically stable outcome with or without sequelae AND the investigator and Medical Monitor agree that the SAE is satisfactorily resolved.
- 5. Inform the Medical Monitor of SAE updates by telephone followed by an SAE form update sent by fax or by e-mail.
- 6. Comply with the appropriate regulatory requirements and Aclaris Therapeutics, Inc. instructions regarding reporting of the SAE to the responsible Institutional Review Board (IRB) or Ethics Committee (EC).

10.2.3. Withdrawal Due to an Adverse Event

Any patient who experiences an adverse event may be withdrawn from study drug at any time at the discretion of the investigator. If a patient is withdrawn wholly or in part because of an adverse event, both the adverse events page and termination page of the CRF will be completed at that time. The patient will be monitored until the event has resolved or stabilized, until a determination of a cause unrelated to the study drug or study procedure is made, or until the patient is referred to the care of a local health care professional. The investigator must inform

Page 43 of 53 Amendment 2 Version 3 Date: 05 December 2017 the medical monitor as soon as possible of all patients who are being considered for withdrawal due to adverse events. Additional reports must be provided when requested.

11. **PREGNANCY**

WOCBP include any female who has experienced menarche and who has not undergone successful surgical sterilization (*e.g.*, hysterectomy, hysteroscopy, bilateral tubal ligation, bilateral oophorectomy or bilateral mini-laparotomy) or is not postmenopausal. Postmenopausal is defined as ≥ 12 months with no menses without an alternative medical cause. Women who are WOCBP and are using an active method of birth control, are practicing abstinence or where the partner is sterile (*e.g.*, vasectomy), should be considered to be WOCBP.

All WOCBP must use an active method of birth control during the course of the study, in a manner such that risk of failure is minimized.

Prior to trial enrollment, WOCBP must be advised of the importance of avoiding pregnancy during trial participation and the potential risk factors for a pregnancy. The subject must sign an informed consent/assent form documenting this discussion. During the trial, all WOCBP will be instructed to contact the investigator immediately if they suspect they might be pregnant (*e.g.*, missed or late menstrual period).

If a subject or investigator suspects that the subject may be pregnant prior to study medication administration, the study medication must be withheld until the results of a pregnancy test are available. If pregnancy is confirmed, the subject must not receive study medication and must be discharged from the study.

If, following study medication administration, it is determined that the subject may have been or was pregnant at the time of study medication exposure (including at least 2 days after study medication administration) the investigator must immediately notify the Medical Monitor and record the event on a pregnancy surveillance form. While not an AE or SAE, the investigator must report every pregnancy using a pregnancy surveillance form and follow the reporting procedures described for SAE reporting (Section 10.2.2).

Protocol-required procedures for trial discontinuation and follow-up must be performed on the subject unless contraindicated by pregnancy (*e.g.*, x-ray studies). Other appropriate pregnancy follow-up procedures should be considered if indicated. In addition, the investigator must report to the Medical Monitor on the pregnancy surveillance form, follow-up information regarding the course of the pregnancy, including perinatal and neonatal outcome. Infants should be followed for a minimum of six weeks.

Page 44 of 53 Amendment 2 Version 3 Date: 05 December 2017

12. STATISTICAL CONSIDERATIONS

12.1. Sample Size and Power Consideration

Based on efficacy results from the previous study and the active study medication specified in the current protocol for the same indication, sample size for the current study is anticipated to provide greater than 90% power to achieve statistical significance in the primary efficacy analysis.

12.2. Statistical Analysis of Efficacy

Primary and secondary efficacy analyses will be performed on the Per-Protocol population, defined as all randomized subjects who missed no more than 3 treatment visits, completed Visit 10 (primary analysis) and Visit 13 (secondary analysis), and who have not had a major protocol violation over that time period, including the use of a clinically relevant quantity of a prohibited medication as determined by the study Medical Monitor. No missing data imputation will be used for these analyses.

Visit 10 is considered to be the primary efficacy endpoint. In addition, some analyses will also be conducted at earlier and subsequent visits, and treated as exploratory analyses. Some sensitivity efficacy analyses may also be re-performed on the Intent to Treat population, defined as those randomized subjects who have at least one post-baseline visit with required efficacy data collection and who completed Visit 10 with required collection of efficacy data. For those analyses, missing efficacy data for intermediate visits will be imputed using the last observation carried forward (LOCF) procedure. A determination as to the performance of analyses using the Intent to Treat population will be based on the number and pattern of visits missed by randomized subjects. Exploratory analyses using models specified below may also be performed for separate age groups, depending on enrollment outcomes.

For all analyses, two-tail alpha will be set to 0.05 with no adjustment for multiple comparisons. ANOVAs and ANCOVAs will include Site in the model only if doing so improves the sensitivity of the model for comparing treatment groups.

After the last randomized subject has completed Visit 10 the database will be validated, locked through Visit 10 and unblinded for the purpose of analyzing efficacy data through Visit 10. Those analyses are not considered to be interim analyses as the results will be final. Data will continue to be collected through Visit 13 for all subjects, and the full database will subsequently be locked for efficacy analysis (including durability of response) beyond Visit 10, and for the analysis of safety and all other clinical data.

The primary efficacy analysis will be a comparison between treatment groups based on the mean change in Target Wart PWA from Baseline (Visit 2) to Visit 10, using Analysis of Covariance with Baseline PWA as the covariate.

Page 45 of 53 Amendment 2 Version 3 Date: 05 December 2017 Secondary efficacy analyses will include comparisons between treatment groups based on the following: the proportion of subjects with the Target Wart Clear (PWA = 0) at Visit 10 using Fisher's Exact Test; the proportion of subjects with all treated warts Clear at Visit 10 using a Cochran-Mantel-Haenszel test stratified by number of treated warts; and the mean of per-subject percentages of treated warts that are clear at Visit 10 using Analysis of Variance. The number of treated warts Clear at Visit 10 will also be analyzed using a Cochran-Mantel-Haenszel test stratified by number of treated warts Clear at Visit 10 will also be analyzed using a Cochran-Mantel-Haenszel test stratified by number of treated warts.

Durability of response in the Active treatment group will be evaluated by calculating the proportion of those treated warts achieving a PWA status of Clear at Visit 10 which continue to maintain a PWA status of Clear at Visit 13. This analysis will be performed separately for Target Warts, and for all treated warts. The 95% confidence limits around the calculated proportions will also be calculated in order to estimate the population lower limit value of the observed sample proportions.

Exploratory analyses will be conducted using a subset of the above analysis models, based on the following baseline wart classifications: warts that are determined to be treatment-naive vs. recalcitrant.

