7.3. Analysis Populations and Disposition of Subjects

7.3.1. Analysis Populations

The Safety Population is defined as all subjects who received at least one application of study medication.

The Intent-to-Treat (ITT) population is defined as all subjects who were randomized, received at least one application of study medication and had at least one post-baseline efficacy evaluation. No data imputation will be used for missing data.

The Per-Protocol (PP) population includes all ITT subjects who completed Visit 10 with no major protocol violation and who missed no more than 3 treatment visits. For the Visit 13 analysis, the PP population must also have had a Visit 13.

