9. STATISTICAL ANALYSIS METHODS

9.1. Statistical Analysis of Efficacy Data

Primary and secondary efficacy analyses will be performed on the Per-Protocol population, defined as all randomized subjects who missed no more than 3 treatment visits, completed Visit 10 (and Visit 13 for purposes of the Visit 13 analysis), and who have not had a major protocol violation over that time period including the use of a clinically relevant quantity of a prohibited medication as determined by the study Medical Monitor. No missing data imputation will be used for these analyses.

Visit 10 is considered to be the primary efficacy endpoint. In addition, some analyses will also be conducted at earlier and subsequent visits, and treated as exploratory analyses. Some sensitivity efficacy analyses may also be re-performed on the Intent to Treat population, defined as those randomized subjects who have at least one post-baseline visit with required efficacy data collection and who completed Visit 10 with required collection of efficacy data. For those analyses, missing efficacy data for intermediate visits may be imputed using the last observation carried forward (LOCF) procedure. A determination as to the performance of such analyses using the Intent to Treat population will be based on the number and pattern of visits missed by randomized subjects. Exploratory analyses using models specified below may also be performed for separate sub-groups, depending on enrollment outcomes.

For all analyses, two-tail alpha will be set to 0.05 unless otherwise specified, with no adjustment for multiple comparisons. ANOVAs and ANCOVAs will include Site in the model only if doing so improves the sensitivity of the model for comparing treatment groups.

After the last randomized subject has completed Visit 10 the efficacy data captured to date in the database will be validated, locked through Visit 10 and unblinded for the purpose of analyzing efficacy data through Visit 10. Those analyses are not considered to be interim analyses as the results will be final. Data will continue to be collected through Visit 13 for all subjects, and the full database will subsequently be locked for efficacy analysis (including durability of response) beyond Visit 10, and for the analysis of safety and all other clinical data.

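### Primary and secondary efficacy rest on a Per-Protocol set formed largely by post-randomisation events, and no Visit 10 efficacy analysis as written can include a subject without Visit 10

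*Protocol*

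**What the plan says.** Protocol 12.2 sets the population: "Primary and secondary efficacy analyses will be performed on the Per-Protocol population". SAP 9.1 repeats this. To be in the set, a subject must have missed no more than three treatment visits, completed Visit 10, and had no major violation. Prohibited medication counts as a violation when the Medical Monitor finds the quantity clinically relevant. Missing data are not imputed.

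The alternative is optional: "Some sensitivity efficacy analyses may also be re-performed on the Intent to Treat population". Whether it is done "will be based on the number and pattern of visits missed by randomized subjects", with no threshold. Three details limit it:

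- In Protocol 12.2 and SAP 9.1 the ITT set is "randomized subjects who have at least one post-baseline visit with required efficacy data collection and who completed Visit 10".
- Carrying forward covers only visits in between. In the SAP, "missing efficacy data for intermediate visits may be imputed using the last observation carried forward (LOCF) procedure"; the Protocol makes this firm rather than optional.
- SAP 7.3.1 defines ITT differently, as "all subjects who were randomized, received at least one application of study medication and had at least one post-baseline efficacy evaluation". It has no Visit 10 condition but rules out imputation.

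The efficacy tables listed in SAP 11 (14.2.1 to 14.2.10) are all Per-Protocol, although that section allows final tables to differ. At withdrawal, Protocol 5.4 asks for reason, date and safety monitoring, and does not mention a Visit 10 PWA.

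The documents also differ on Visit 13. Protocol 12.2 ties it to the secondary analysis, yet the secondary between-group comparisons are at Visit 10. SAP 9.1 requires it only where it is needed: "and Visit 13 for purposes of the Visit 13 analysis".

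**The concern.** This is a vehicle-controlled superiority comparison. Randomisation protects it only if leaving the analysis set is unrelated to outcome. Protocol 5.3 lists adverse events, unwillingness to continue and prohibited medication among the reasons for removal, and a wart that does not clear could prompt the last two.

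Two kinds of exclusion need separating. Subjects removed for missed treatments or violations, but seen at Visit 10, would return in the ITT rerun if someone chose to run it. Subjects with no Visit 10 would not return in any written Visit 10 efficacy analysis. The plan therefore commits to no analysis that would show whether the first kind matters, and contains none for the second. Visit 10 results are unblinded and declared final, so the analysis set cannot credibly be changed afterwards.

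**Working it through.** **1. The plan's own figure.** Protocol 12.1 claims more than 90% power but gives no effect, SD or loss rate, so the figure cannot be reproduced. With 60 per arm and two-sided 0.05, 90% power needs a standardised difference of (1.960 + 1.282) × √(2/60) = 0.592 (0.597 with the t distribution).

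**2. Who can enter a Visit 10 efficacy analysis.**

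| Dosed subject | Per-Protocol | ITT, Protocol 12.2 and SAP 9.1 | ITT, SAP 7.3.1 |
|---|---|---|---|
| Visit 10 done, more than 3 treatments missed | out | in, if rerun chosen | in, if rerun chosen |
| Visit 10 done, major violation | out | in, if rerun chosen | in, if rerun chosen |
| No Visit 10, some post-baseline PWA | out | out | in the set, but no Visit 10 value |
| No post-baseline PWA | out | out | out |

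The primary ANCOVA uses only baseline and Visit 10, so filling intermediate visits cannot alter it.

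**3. Possible size (illustration).** Every rate here is an assumption.

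- There is no true effect, with 60 per arm.
- Baseline PWA 2:3 is 60:40.
- Visit 10 clear/near-clear rates are 5/15, 10/20 or 20/20%. One fifth of the remaining grade 3 warts fall to grade 2.
- A non-improver has Visit 10 PWA not below baseline (here, change 0).
- Losses of 5, 10 and 15% are 3, 6 and 9 of 60.

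If a fraction f of an arm is lost and all are non-improvers, the arm mean change μ becomes μ/(1 − f), a shift of μf/(1 − f). For the 10/20 mix:

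- Baseline 2: −2 × 0.10 − 1 × 0.20 = −0.40.
- Baseline 3: −3 × 0.10 − 2 × 0.20 − 1 × 0.14 = −0.84, where 0.14 = 0.70 × 0.2.
- μ = 0.6 × (−0.40) + 0.4 × (−0.84) = −0.576.
- With f = 0.15, the shift is −0.576 × 0.15/0.85 = −0.102 grade. Simulation with the baseline covariate gives about −0.10.

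Now let non-improvers be only twice as likely to be lost. Their share is 0.6 × 0.70 + 0.4 × 0.56 = 0.644. Of 9 losses, about 9 × 1.288/1.644 = 7.05 are non-improvers and 1.95 are improvers. Improvers number 60 × 0.356 = 21.36, with mean change −0.576/0.356 = −1.618. The remaining mean is (21.36 − 1.95) × (−1.618)/51 = −0.616, a shift of −0.04. If both arms lose the same way, the shifts cancel.

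Simulated ANCOVA results across the three mixes (negative favours active):

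| Loss, active v vehicle | Bias, grades | Two-sided type I error |
|---|---|---|
| None | 0.00 | 4.9–5.1% |
| 10% v 10%, random | 0.00 | 4.9–5.1% |
| 10% v 10%, all non-improvers | 0.00 | 5.2–6.1% |
| 15%, non-improvers twice as likely, v 5% random | −0.03 to −0.05 | about 5.4–6% |
| 15%, all non-improvers, v 5% random | −0.065 to −0.137 | 7.9–11.8% |
| 5% random v 10%, all non-improvers | +0.04 to +0.09 | 6.2–7.9% |

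The twofold row comes from shorter runs, with a Monte Carlo standard error of about 0.3 points.

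**4. What the optional rerun would recover.** Take the extreme row, with 9 active and 3 vehicle exclusions. If 3 and 1 of them have Visit 10, bias is still −0.041 to −0.086 (6.1–8.1%). If 6 and 2 have it, bias is −0.019 to −0.041 (5.1–5.9%).

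**The case against.** The strongest case against is that nothing in the documents shows a bias. The solutions look alike (Protocol 7.1), and the earlier study reported good tolerability (Protocol 2.2). A persistent wart acts equally in both arms when the drug does nothing. If the drug works, vehicle has more persistent warts, so loss for that reason would tend to count against active. Inflation in favour of active needs loss that differs by arm. The largest figures need, in addition, that every active loss is a non-improver. All of this stands, and it limits what can be said about size.

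The plan also covers part of the ground. Protocol 8.3 requires PWA at every study visit, and collection continues to Visit 13, so subjects who stop drug but stay in the study already have a Visit 10 assessment. Protocol 5.4 needs only a clarification. The ITT rerun, if done, would recover those subjects.

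This does not answer the structural point. The rerun is discretionary, and the two ITT definitions conflict.

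A reader might infer that subjects without Visit 10 vanish from every analysis. They do not. The safety summaries in SAP section 8 use everyone dosed, and an optional earlier-visit rerun on the SAP 7.3.1 set could include them. Nor is Per-Protocol membership wholly post-randomisation: entry-criteria violations (Protocol 13.2) are fixed at baseline and are not part of this point.

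**Conclusion.** The point holds for Visit 10 efficacy. The primary and secondary comparisons use a set that depends largely on post-randomisation events. The only alternative is optional, and no written Visit 10 efficacy analysis can include a subject without Visit 10. This follows from the text and needs no simulation.

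The size and direction of any bias cannot be derived, because no exclusion rates or reasons by arm are given; it may be near zero. Under the assumptions shown, type I error is 5 to 6% with symmetric loss, about 5.4 to 6% with moderate arm-specific selection, and about 8 to 12% only in the extreme case. A reader might take that last range as the expected inflation, or conclude that the plan favours active. The documents support neither, and loss in the other direction is equally possible.

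**What to change.** Change Protocol 12.2 and SAP 7.3.1, 9.1 and 11, with the clarification in Protocol 5.4, before the Visit 10 unblinding:

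1. Use one ITT definition: all randomised subjects who received at least one application, analysed as randomised, with no Visit 10 condition. Make it the mandatory primary efficacy set. This fits Protocol 5.5, which replaces undosed subjects.
2. Keep Per-Protocol as supportive, with membership fixed blinded. Adopt the SAP wording that needs Visit 13 only for the Visit 13 analysis.
3. Keep the ANCOVA with baseline PWA. Handle missing Visit 10 PWA by one pre-specified method, for example multiple imputation by arm from baseline and Visit 3–9 PWA. Use the same imputations for the per-subject percentage and percent-change endpoints.
4. Count a missing or unassessable Visit 10 as non-response for all Clear, Clear/Near-Clear and all-warts responder endpoints.
5. Use PWA recorded after prohibited therapy as observed in the primary ITT analysis. In a sensitivity analysis, count such subjects as non-responders for the responder endpoints.
6. Add a tipping-point analysis that worsens imputed active-arm values up to grade 3, the top of the scale. Imputation alone does not remove bias when loss depends on the unseen Visit 10 value. Before that cap, a one-grade penalty moves the difference by 6/60 = 0.10 with 6 missing, or 9/60 = 0.15 with 9.
7. Drop LOCF and add ITT versions of Tables 14.2.1–14.2.7.
8. Clarify in Protocol 5.4 that subjects who stop treatment but agree to attend have PWA recorded at the already scheduled Visit 10.

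The cost is wording, modest programming and visits already scheduled. The estimate may be smaller and power slightly lower. If the Per-Protocol effect were 0.597 SD, a 5% or 10% smaller effect with 60 dosed per arm gives 86.9% or 83.1% power. If more are dosed to reach 60 evaluable (60/0.95 ≈ 64, 60/0.90 ≈ 67 per arm), it is 88.9% or 87.0%. These figures ignore information lost to imputation. Restate the power for this set rather than enrolling more subjects.
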